## Analytical methods

Satisfaction with the PMSB treatment was measured using six questions from the 12-month follow-up assessment. Three of these questions asked about satisfaction with the Positive Minds sessions, and three about satisfaction with the Strong Bodies sessions. A sample item from these six questions was “*How satisfied or unsatisfied were you with the care you received from the Exercise Trainer?*” Response options were 1 (*very unsatisfied*), 2 (*not that satisfied*), 3 (*somewhat satisfied*), and 4 (*very satisfied*).

We first analyzed the means, variances, skewness/kurtosis, and minimum and maximum values for the satisfaction questions. Although participants could choose among four options ranging from 1 (*very unsatisfied*) to 4 (*very satisfied*), the distributions were skewed, suggesting that the primary decision among participants was whether they were *very satisfied* with the sessions. To account for these extreme distributions, we recoded the questions to be binary (with values 1, 2 and 3 coded as zero, and 4 coded as one) and created a single satisfaction measure as the mean of these six binary variables (scale ranges from 0 to 1), such that higher values represent a higher proportion of participants who were *very satisfied*.

We carried out descriptive analysis to examine patterns of missing data and how they were related to sample baseline characteristics. We defined two types of missing data: complete missing (if a specific follow-up assessment was missing because of participant withdrawal or lost-to-follow-up) and partial missing (when follow-up assessments were conducted but variables were missing due to “refused to answer” or “don’t know” responses). Because most data were complete missing, we examined baseline characteristics between participants who completed all follow-up assessments versus those who missed at least one.

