Although missing a follow-up assessment did not seem to be related to participants’ demographic characteristics, to account for missing data we used multiple imputation methods in Stata version 15.1 via the *mi impute chained* command (5). Multiple imputation was carried out in three steps. First, we imputed the missing data for all the variables considered, creating 20 imputed datasets each one consisting of 307 participants with three follow-up assessments per participant. In the second step we ran analysis on each individually imputed data set. Finally, we aggregated the individual estimates to obtain final estimates and adjusted standard errors for the uncertainty due to imputation (6).

Each imputation was carried out using the chained equations method (7). In what follows, we refer to variables with missing data as incomplete variables and those with non-missing data as complete variables. Each incomplete variable  $x_j$  was specified as a conditional function ( $g_j$ ) given the set of all other variables used in the imputation, comprising both incomplete ( $x_1, \dots, x_m$ ) and complete variables ( $Z$ ). We fitted the conditional model  $g_j$  to generate the predicted values of  $x_j$  using an iterative method. Specifically, each incomplete variable  $x_j$  was iteratively estimated and in each iteration the variable  $x_j^t$  was then updated to  $x_j^{t+1}$  based on the conditional model. This updated variable was then used in the estimations of the other variables, following the conditional model specification

$$x_j^{t+1} \sim g_j(x_j \mid x_1^{t+1}, \dots, x_{j-1}^{t+1}, x_{j+1}^t, \dots, Z, \phi_j),$$

for  $j \in \{1 \dots m\}$ , where  $\phi_j$  were parameters of the conditional model  $g_j$ . These steps were repeated for all variables  $x_1, \dots, x_m$  and, after an initial burn-in phase, the procedure was stopped once convergence was reached.

The variables used for imputation included main outcome variables and their baseline measures, participant socio-demographics, clinical characteristics, and study design variables, such as site and intervention indicators, as well as dummy indicators for each follow-up assessment.

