We used interval regressions to incorporate the theoretical bounds of the clinical outcome variables to increase the efficiency and accuracy of the imputation procedure (e.g., we restricted the imputed values of PHQ-9 to lie within the 0 to 27 intervals). We used logistic regression models to impute binary variables, and linear regression models to impute continuous variables.

For Analysis, first, we compared distributions of baseline characteristics between participants who received the PMSB intervention and participants in the usual care group, to assess the balance of the observed covariates. For each follow-up assessment, we compared the baseline covariates to detect any significant baseline differences between those who completed assessment versus those who did not.

Second, to assess the effect of the intervention, we conducted an intent-to-treat (ITT) analysis, using a multilevel, multivariate regression model to assess changes in outcome variables over time in the treatment and control groups. To account for the nature of longitudinal data, the ITT analysis was carried out by fitting multilevel mixed-effects models to allow for valid variance calculation and statistical inference. The multilevel models computed included random effects at both participant- and site-level to account for within-participant and within-site correlations, as well as robust clustered standard errors to account for within-site correlations due to participants nesting within same site. Letting  $Y_{itj}$  denote the outcome measured at time  $t$  after the baseline for participant  $i$  at site  $j$ , we estimated the following model:

$$(1) \quad Y_{itj} = \beta_{0i} + \beta_{0j} + \beta_1 Intervention_i + \beta_2 Time_t + \beta_3 Intervention_i \times Time_t + \beta_4 (Time_t - t^*) + \beta_5 Intervention_i \times (Time_t - t^*) + \beta_6 X_i + \varepsilon_{itj}$$

where the participant-specific random intercept can be written as  $(\beta_{0i} = \alpha_{00} + \omega_{0i})$  and the site-specific random intercept can be written as  $(\beta_{0j} = \gamma_{00} + \epsilon_{0j})$ . We fitted only linear models as all our outcomes were continuous.

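### The imputation layout is not stated; on its most natural reading (one row per visit) it omits the arm-by-time and within-participant structure that equation (1) tests

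*Combined protocol and SAP*

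**What the plan says.** All references are to Analytical methods in the combined protocol and SAP.

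- **Data sets.** Twenty imputed data sets were made, "each one consisting of 307 participants with three follow-up assessments per participant". Then "we ran analysis on each individually imputed data set", and the estimates were pooled.
- **Imputation equations.** Only the generic form is given: each incomplete variable is modelled "given the set of all other variables used in the imputation". The variable classes are outcomes and their baseline values, socio-demographics, clinical characteristics, and design variables such as site and arm, "as well as dummy indicators for each follow-up assessment".
- **Regression families.** Bounded clinical outcomes used interval regression. Otherwise: "We used logistic regression models to impute binary variables, and linear regression models to impute continuous variables".
- **Type of missingness.** Missed visits dominate: "Because most data were complete missing", completers of all visits were compared with the rest on baseline characteristics. For each follow-up, "we compared the baseline covariates to detect any significant baseline differences between those who completed assessment versus those who did not".
- **Analysis model.** Equation (1) has participant and site random intercepts and arm-by-time terms before and after month 6. β1 is the 6-month effect. β3 and β5 test differences in change over time, and the 12-month effect is built from interactions. The plan itself expects that the effect may fade after treatment stops.

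**The concern.** Dummies for each follow-up do useful work mainly in a file with one row per participant-visit. In a file with one row per participant they would be constant, unless they record attendance. If the file was stacked with the listed terms only, a missed visit has almost no same-visit scores to borrow from. It is filled from baseline, covariates, site, arm and visit, with a single arm effect for all visits.

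Two things are then missing from the imputation but present in equation (1):

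- **Arm-by-visit terms.** Without them, imputed rows pull each visit's effect towards the average effect.
- **Within-participant correlation.** Without it, imputed rows add noise to within-person contrasts, so reported standard errors for β3 and β5 exceed the true spread.

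At stake is whether a null β3 or β5, or an apparent 12-month benefit, reflects the data or the imputation. The plan describes no safeguard. The missingness checks use baseline characteristics and not earlier follow-up scores, and none of the four sets of sensitivity analyses is described as varying the imputation or using observed data only.

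**Working it through.** **Inputs from the plan.** 307 participants, three follow-ups, 20 imputations, and Time coded −4/0/6. For SPPB, LLFDI and WHODAS 2.0, 70 participants are excluded: 307 − 70 = 237.

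**Assumed.** The plan gives no missing rates, effect sizes or correlations, so it has no figure to reproduce. Effects are in SD at months 2/6/12, within-person correlation is 0.6, data are missing completely at random, and the spline knot is at month 6 as intended.

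**Step 1: bias on the stacked reading.** Let r_t be the observed fraction and d_t the true effect at visit t. With arm and visit main effects only, the expected effect in the imputed data is r_t·d_t + (1 − r_t)·D, where D = Σ(r_t·d_t)/Σr_t.

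| True effects | Missing | D | Effects in imputed data |
|---|---|---|---|
| 0.1/0.4/0.2 | 20/20/20% | 0.233 | 0.127/0.367/0.207 |
| 0.3/0.3/0 (fading) | 10/20/30% | 0.2125 | 0.291/0.283/0.064 |
| 0.2/0.3/0.45 (growing) | 10/20/30% | 0.306 | 0.211/0.301/0.407 |

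Example for the fading row at month 12: 0.7 × 0 + 0.3 × 0.2125 = 0.064, where the truth is 0. In the growing row, 0.45 becomes 0.407, about 10% too small. The 6-month effect moves by −0.033 in the first row, about a third of its reported standard error of 0.102.

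**Step 2: β3 and β5.** β3 = (d6 − d2)/4 and β5 = (d12 − d6)/6 − (d6 − d2)/4. For the first row:

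- β3: truth 0.3/4 = 0.075; imputed (0.367 − 0.127)/4 = 0.060.
- β5: truth −0.033 − 0.075 = −0.108; imputed −0.027 − 0.060 = −0.087.

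Both shrink by 20%, the missing rate. With equal missingness at every visit the shrinkage always equals that rate.

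**Step 3: power at n = 307.** Simulation of the first row (1,500 replicates, Monte Carlo error about 1.3 points for power) gave these values for β3:

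- Stacked: reported SE 0.0318, sampling SD 0.0240.
- Observed-data likelihood: reported SE 0.0294, sampling SD 0.0290.

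A normal approximation reproduces the simulated power:

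- Stacked: the critical value is 1.96 × 0.0318 = 0.0623; Φ((0.060 − 0.0623)/0.0240) = 46%. Simulated: 46% (β5: 45%).
- Likelihood: the critical value is 1.96 × 0.0294 = 0.0576; Φ((0.075 − 0.0576)/0.0290) = 73%. Simulated: 73% (β5: 73%).

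Wide imputation gave 72% for β3 and 71% for β5. A second simulation gave 45% against 69% for β3 and 44% against 69% for β5. Rounded, this is about 45% against 70%.

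**Step 4: n = 237.** Standard errors grow by √(307/237) = 1.138. The same approximation gives 34% stacked and 61% likelihood for β3, in line with simulated values of about 33% against 60% (stacked against wide).

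**Step 5: low missingness.** At 5–10% missing and n = 307, power is about 71% stacked against 79% wide.

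**Step 6: test size.** The ratio 0.0318/0.0240 = 1.325 implies that a nominal 5% test rejects when |z| > 1.96 × 1.325 = 2.60, about 1% of the time. Simulation with a constant effect and 10/20/30% missing gave 1.0% for β3 and 1.2% for β5.

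**The case against.** The strongest reply is that no error has been shown. The variable list is introduced as examples, and the follow-up dummies could be attendance indicators in a wide file. With wide imputation the problem disappears, and what remains is a reporting gap. That stands: a reader might infer that the imputation was certainly stacked, and the documents do not establish it. They do make it the most natural reading.

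Second, the main hypothesis is hardly touched. β1 is unbiased under a constant effect and moves little otherwise. In the 20% case stacked imputation has root mean squared error no worse than wide for β1 (0.0961 against 0.0973), β3 (0.0282 against 0.0292) or β5 (0.0408 against 0.0421). This also stands. The harm is shrinkage and conservative tests of change over time, not a larger overall error.

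Third, a reader might infer that an overstated 12-month effect means more false-positive claims at 12 months. This is not established. For the 0.3/0.3/0 pattern, simulated rejection rates at a nominal 5% ranged from 5.4% to 7.1% across set-ups; for 0.1/0.4/0 they were between 3% and 5%. The bias reproduces, but inflation of the error rate does not do so reliably.

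Fourth, the simulations left out site effects, site-clustered standard errors and score bounds, all of which the plan uses. The exact power and size figures are therefore indicative only. A worry about the logistic imputation steps has little force, since the plan states: "We fitted only linear models as all our outcomes were continuous". Those steps would concern incomplete binary covariates only.

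**Conclusion.** The point holds conditionally. The layout and the actual imputation terms are not stated. If visits were stacked with the listed terms, the imputation is poorer than equation (1) in exactly the features that β3, β5 and the 12-month effect depend on.

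The direction at month 12 depends on the true pattern: overstatement if the effect fades, understatement if it grows, none if it is constant. The cost to the β3 and β5 tests is material at around 20% missing and modest at 5–10%. The n = 307 figures apply to HSCL-25 and GAD-7, and the n = 237 figures to the three physical-function outcomes. All sizes rest on the assumed effects, missing rates and correlation. The documents do not support a conclusion that the 6-month result is invalid.

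**What to change.** 1. State the layout, the terms of each imputation equation, and the number of missing assessments by arm and visit.
2. Add, for each of the five outcomes, a likelihood fit of equation (1) to the observed data as a sensitivity analysis. The printed spline coding must be corrected first: with Time at −4/0/6 and t* = 6, Time never exceeds t*, so the spline term is zero at every visit and β5 cannot be estimated. The printed 12-month expression, which uses β2 and β3 but not β5, needs correcting with it.
3. If the imputation was stacked, re-impute in wide form. Model each follow-up of an outcome on that outcome's other visits, its baseline, arm, site and a trimmed covariate set, and keep the score bounds. Then reshape to long. Arm as a predictor in each visit's equation already gives every visit its own arm effect, so separate imputation by arm is optional.

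**Cost.** No new data: one extra fit per outcome and possibly one re-run of the imputation. The downside is a slightly larger sampling SD for β1 (0.097 against 0.091 in the 20% case) with no gain in its root mean squared error. The gain is removal of the pull towards the average effect, and tests of change over time that were close to their nominal size in the simulated settings.

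### Partly answered scales go through the same imputation as missed visits, bounded only by the full scale range, so if one unanswered item sets a total to missing, the answered items are ignored

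*Combined protocol and SAP*

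**What the plan says.** All of the relevant text is in the Analytical methods section of the combined protocol and SAP.

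- **Two kinds of missing data.** Complete missing means that the follow-up assessment did not take place. The other kind is "partial missing (when follow-up assessments were conducted but variables were missing due to “refused to answer” or “don’t know” responses". No counts are given, only the remark "Because most data were complete missing, we examined baseline characteristics".
- **One imputation for both.** Chained equations are used, "creating 20 imputed datasets each one consisting of 307 participants with three follow-up assessments per participant". Each incomplete variable "was specified as a conditional function" of all the others.
- **Predictors.** "The variables used for imputation included main outcome variables and their baseline measures, participant socio-demographics, clinical characteristics, and study design variables", such as site and arm, plus indicators for each follow-up. Item responses are not listed.
- **Bounds.** "We used interval regressions to incorporate the theoretical bounds of the clinical outcome variables", with this example: "we restricted the imputed values of PHQ-9 to lie within the 0 to 27 intervals". No narrower bounds are mentioned for a scale that was partly answered.

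The section does not say when a scale total counts as missing, whether totals are prorated, or how many scores were partly missing.

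**The concern.** Refused and don't-know are answers to questions, so for a multi-item scale the likely event is that some items were answered and others were not. The answered items then restrict the total to a narrow range. An imputation that knows only the full scale range and a prediction from other variables can give an assessed participant a total that their own answers rule out. These values enter the intent-to-treat models.

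The plan justifies the theoretical bounds as improving the efficiency and accuracy of the imputation. For partly answered scales, the answered items would serve that aim far better: one missing PHQ-9 item leaves a window 3 points wide, against 27 for the scale. What is at stake is recorded information. Long scales are the most exposed, if a single unanswered item is enough to set the total to missing.

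**Working it through.** **Inputs.** From the plan: the 0 to 27 range for PHQ-9, the predictor list, and the statement that most missing data were complete missing. Assumed: nine items scored 0 to 3, and the means, item correlations and explained variances given below.

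**The plan's figure.** 9 × 3 = 27, so the stated range agrees with the assumed scoring.

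**Feasible window.** With answered sum S and k items unanswered, the total lies in [S, S + 3k]. The width is 3 points for k = 1, 6 for k = 2 and 9 for k = 3.

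**One record.** Eight items sum to 14, so the total is 14 to 17. Let the model predict 8 with residual SD σ. For a normal draw truncated to 0–27,

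share outside = 1 − [Φ((17−8)/σ) − Φ((14−8)/σ)] / [Φ((27−8)/σ) − Φ((0−8)/σ)].

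- σ = 3.0: 1 − 0.0214/0.9962 = 97.9%
- σ = 3.5: 1 − 0.0382/0.9889 = 96.1%
- σ = 4.5: 1 − 0.0685/0.9623 = 92.9%

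This record was chosen with answers well above the prediction, so it illustrates the mechanism and is not typical.

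**The most favourable case.** If the prediction sits at the centre of the window (ignoring truncation), more than half of the draws fall outside once σ exceeds 1.5k/0.6745: 2.22 for k = 1, 4.45 for k = 2 and 6.67 for k = 3.

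**Average over records.** Nine correlated items were simulated with mean total 5, 8 or 11, item loading 0.60 or 0.75, and 20%, 40% or 60% of the total's variance explained by other variables. Items were missing at random, and draws came from a normal truncated to 0–27.

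| Items missing | Draws outside the window | After rounding to integers |
|---|---|---|
| 1 | 65–85% | 55–81% |
| 2 | 40–70% | 32–65% |
| 3 | 26–54% | 20–50% |
| 4 | 18–39% | 14–36% |
| 5 | 12–27% | 9–24% |

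**Error per record, one item missing.** In a similar simulation (mean 8, SD 5.7, explained variance 30–70%), the root mean square error was 4.3–6.5 points with scale bounds and about 1.5 with record-specific bounds. Record-specific bounds alone still overshoot, by about 0.8 points per record in one set-up; prorating the answered items there gave no average error and a root mean square error of 0.85.

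**Share of all imputed totals.** If fewer than half of the missing scores are partial, the infeasible share of all imputed totals is below 50% even if every partial draw is infeasible. With illustrative partial shares of 10% and 25%, and 80% of those draws infeasible, it is 0.10 × 0.80 = 8% and 0.25 × 0.80 = 20%.

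**Precision.** Take the information lost as the share of visit scores that are partial × (1 − R²), with R² = 0.5. Partial shares of 5% and 10% (assumed) lose 2.5% and 5%. The standard error grows by 1/√0.975 − 1 = 1.3% and 1/√0.95 − 1 = 2.6%.

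**The case against.** The strongest reply is that the key step is inferred. The plan speaks of missing variables, not items, and never says that one unanswered item sets a total to missing. If totals were prorated and only largely unanswered scales were imputed, the problem nearly disappears. The reference list also includes sources for the scales that the available text never cites, so a measures section may exist elsewhere. The 0 to 27 range is an example of an outer limit, and interval regression accepts bounds per record, so narrower bounds are not excluded. PHQ-9 is not among the five outcomes in the joint model. All of this stands, and it makes the point conditional. It does not remove it: the written method gives no scoring or item-level rule, and its bounds sentence covers clinical outcomes generally, which would include GAD-7 and HSCL-25.

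A reader might also infer more than the text supports:

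- *That values are drawn freely over the whole scale.* They are drawn conditionally on other outcomes, baseline measures and design variables; the scale range is only the limit.
- *That most imputed totals are impossible.* This cannot hold across all imputed totals if partial records are a minority. Within partial records it holds for one missing item, is uncertain for two, and generally fails for three or more.
- *That the treatment effect is biased.* This would need, for example, refusal related to symptoms in a way that differs by arm. Nothing in the plan shows that. Wider between-imputation variance reflects the unused information and does not by itself invalidate the inference.

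**Conclusion.** The point holds in conditional form. As written, the plan distinguishes partly answered from missed assessments and then does not use the distinction in the imputation. If unanswered items set totals to missing, information already collected is discarded, and with one PHQ-9 item missing the majority of draws contradict the answers in every scenario tried.

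The consequence for the trial is a modest loss of precision: a standard error about 1–3% larger if 5–10% of visit scores were partial. That share is an assumption, since the plan gives no count. The percentages also rest on 0 to 3 item scoring and on the simulated correlations. They apply to PHQ-9 and do not transfer directly to scales whose scoring the plan does not give. The change is still worth making, because it is cheap and gives more precise values for participants who were assessed.

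**What to change.** In the bounds paragraph of the Analytical methods:

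1. Keep the theoretical bounds for assessments that were missed altogether.
2. For partly answered item-summed scales, use the answered items. Preferably impute the missing items and then sum them, or include the answered-item score as a predictor of the total.
3. At minimum, give the interval regression record-specific bounds: the answered sum plus the lowest, and plus the highest, possible score on the unanswered items (S to S + 3 for one PHQ-9 item under 0 to 3 scoring). This removes infeasible values but, because of the overshoot shown above, is the weaker option.
4. For an outcome that is not a simple item sum, impute the missing component.
5. State the scoring rule for incomplete scales and the number of partly missing scores per outcome, visit and arm. If item-level information was already used, saying so settles the point.

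The cost is a few sentences, modest programming from item-level data (two derived bound variables per scale for the minimum version), and a rerun of the imputation and the models that depend on it. No new data are needed. Item-level imputation adds equations to the chained model, most of all for HSCL-25; the answered-item score as a predictor is the lighter alternative there.

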## Descriptive methods

The Positive Minds component (adapted from the CERED manualized intervention) is a psychosocial intervention that utilizes psychoeducation and cognitive behavioral therapy (CBT) to treat symptoms of depression and anxiety, including noticing and overcoming unhelpful thoughts. It also presents a range of mindfulness practices, communication techniques, and behavioral activation, by engaging the participant in pleasant activities, and encouraging supportive relationships. Sessions are tailored to the participant's needs using a collaborative approach. The 10-session intervention is culturally adapted for use among a wide group of minority elders and conducted in the participant's language of preference (English, Spanish, Cantonese or Mandarin). Community Health Workers used motivational enhancement strategies to engage the participants. The 10 one-hour sessions were completed over a 6-month period. Every other week the CHWs evaluated participants with the PHQ-9 and GAD-7 and, if necessary, the 5-item Paykel suicide questionnaire, both for participant safety and to ensure the participant's mental health was not deteriorating to the point where immediate intervention or referral was necessary. As part of an emergency protocol, we connected participants to an emergency responder as required. This symptom assessment was administered for both intervention and enhanced usual care groups.

Participants were simultaneously offered the Strong Bodies exercise sessions. Group sessions with an Exercise Trainer (3-5 elders per group) were provided 3 times per week for 12-14 weeks, for a total of 36 sessions. The functional disability prevention component of the Strong Bodies intervention emphasizes building resistance or power training. The intervention consists of a series of exercises that are conducted while wearing a weighted vest. Resistance progresses in 2% body weight increments and weights were distributed evenly within the vests.

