To decrease barriers to engagement in the combined intervention, we designed the program to be deliverable both in person and over the phone. Study participants assigned to receive the Strong Bodies intervention were offered an instructional video of the exercises for at-home use. If participants were unable to attend the small-group exercise sessions in-person 3 times per week for 12 weeks, they received training from their Exercise Trainer to use the instructional video and perform the exercises at home. The video was intended to supplement the in-person classes and provide an opportunity for participants to engage in exercises when they are unable to attend the class in person. To this end, we discussed important considerations for phone delivery during the training of study clinicians. For instance, we discussed the need to ask participants whether they were in a private place with no distractions, the importance of vocal intonation, referring to the participant manual, and verbal affirmations to convey empathy.

Community Health Workers (CHWs) deliver the Positive Minds component of the intervention. We drew on the Bureau of Labor Statistics model of CHWs who "implement programs in the community that promote, maintain, and improve individual and community health" (Standard Occupational Classification 21-1094 Community Health Workers. 2017; <https://www.bls.gov/oes/2017/may/oes211094.htm>)

CHWs were selected and trained from each collaborating community-based organization (CBO) and the Disparities Research Unit. Each CBO had a designated site leader who oversaw the intervention process locally. Part of the Site Leaders' role was to identify staff – either within the organization or identified externally – who would carry out the CHW position. Our recruitment criteria included identifying individuals with work experience that was relevant to the intervention; who were bilingual/bicultural; and who exhibited interpersonal skills in communication, trust, warmth and rapport-building.

We devoted significant time to training the CHWs to offer the clinical intervention at the study sites. Over a four-month period, they were trained on the core elements of the intervention and on understanding the skills and objectives of the intervention. CHWs began with a 2-day training including didactic instruction and role play. The training included two intensive days of workshops and practice sessions, including

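### Site-clustered standard errors would not cover health workers who treated at more than one site, and no small-sample reference is named; add a partially nested sensitivity analysis

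*Combined protocol and SAP*

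**What the plan says.** Analytical methods specifies, for equation (1), "random effects at both participant- and site-level to account for within-participant and within-site correlations". The same sentence continues "as well as robust clustered standard errors to account for within-site correlations due to participants nesting within same site". Equations (1) to (3) contain no health-worker or exercise-group term, and none of the planned sensitivity analyses addresses clustering by provider or group. The text names no small-sample correction for the clustered errors. The last item in the reference list concerns small-sample degrees of freedom, but by its title for multiple imputation, and the analysis text does not cite it.

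On delivery, Descriptive methods says "Group sessions with an Exercise Trainer (3-5 elders per group) were provided 3 times per week for 12-14 weeks" and "Community Health Workers (CHWs) deliver the Positive Minds component of the intervention". On where the workers came from: "CHWs were selected and trained from each collaborating community-based organization (CBO) and the Disparities Research Unit". The same section says the program could be delivered in person or by phone. It also says "Every other week the CHWs evaluated participants with the PHQ-9 and GAD-7", and then "This symptom assessment was administered for both intervention and enhanced usual care groups".

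The number of sites, health workers and groups, the caseloads and any ICC are not given.

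**The concern.** Participants were randomised individually, but the delivered treatment is clustered. Intervention participants share a therapist and may share an exercise group, while control participants receive neither component. If outcomes of participants with the same worker or group are correlated, the intervention-arm mean is less precise than independent observations would suggest, and a participant-plus-site model has no term for this.

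A variance clustered on site is valid only if all correlation lies within sites. Exercise groups that meet at a site satisfy this. A health worker treating at several sites does not, because the sites then share a source of variation that the estimator treats as independent. Intervals would be too narrow and the type I error above 5%, for all outcomes if the worker effect reaches all of them.

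**Working it through.** **Inputs from the documents.** 307 participants; allocation taken as 1:1 from the two-person blocks; exercise groups of 3-5; 70 exclusions for physical function outcomes, leaving 307 - 70 = 237. The plan gives no power, alpha or ICC figure to reproduce.

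**Assumptions.** Worker ICC 0.02-0.05; m = 15 participants per worker; J = 6-15 sites; site ICC 0.03; equal site sizes; one time point.

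**Step 1: model-based errors alone.** The design effect in one arm is 1 + (m - 1) x ICC, and the true SE divided by the naive SE is sqrt((1 + deff)/2).

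- ICC 0.02: deff = 1 + 14 x 0.02 = 1.28; ratio sqrt(2.28/2) = 1.068; two-sided alpha 6.6%.
- ICC 0.05: deff = 1 + 14 x 0.05 = 1.70; ratio sqrt(2.70/2) = 1.162; alpha 9.2%.
- Groups of 4 with group ICC 0.05-0.15: deff 1.15-1.45; alpha 5.9-7.7%.

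These figures would apply only if the plan relied on model-based errors. It does not.

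**Step 2: site-robust errors, all clustering within site.** With groups of 4 (ICC 0.05) and worker caseloads of up to 10 (ICC 0.02-0.05) nested in sites, 4,000 simulated null trials per setting gave robust SE / true SE of 0.98-1.03. A t reference on J - 1 rejected 4.5-5.5%. The site-robust variance absorbs nested clustering.

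**Step 3: some workers cross sites.** Let p be the share of intervention participants treated by a cross-site worker, and suppose that the site-robust variance misses those workers' contribution. Then robust SE / true SE is about

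r = sqrt{[2 + (1 - p)(m - 1)ICC] / [2 + (m - 1)ICC]},

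and the corrected test rejects with probability P(|T| > r x t), where T has J - 1 degrees of freedom and t is its 97.5% point.

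| Worker ICC | p | r | Type I error, J = 6 to 15 |
|---|---|---|---|
| 0.02 | 25% | sqrt(2.21/2.28) = 0.985 | 5.3% |
| 0.02 | 50% | sqrt(2.14/2.28) = 0.969 | 5.5-5.7% |
| 0.02 | 100% | sqrt(2.00/2.28) = 0.937 | 6.1-6.4% |
| 0.05 | 25% | sqrt(2.525/2.70) = 0.967 | 5.5-5.7% |
| 0.05 | 50% | sqrt(2.35/2.70) = 0.933 | 6.2-6.5% |
| 0.05 | 100% | sqrt(2.00/2.70) = 0.861 | 7.8-8.6% |

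Simulation agrees: 4.8-6.4% at 25-50% crossing and 5.8-9.0% at full crossing. Repeat runs under similar settings reached 7.2% at 50% and 9.1% at 100%. Monte Carlo error is a few tenths of a point.

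**Step 4: the reference distribution.** With no crossing, comparing the site-robust statistic with 1.96 rejects with probability of about P(|T| > 1.96) on J - 1 degrees of freedom: 10.7% for 6 sites, 8.2% for 10 and 7.0% for 15. Simulated rates were 9% at 8 sites and 7-8% at 12, and nearly the same with no worker or group clustering at all. This inflation is separate from Step 3.

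**The case against.** The strongest reply is that the plan's own sentence answers the concern. Site-clustered errors allow any correlation within a site, including correlation confined to one arm, and Step 2 confirms it. Each community organization had a site leader who oversaw the intervention locally and identified staff for the role, so most workers were probably nested. With a minority crossing, the corrected test stays near 5%.

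Most of this stands. A reader might infer from the omitted terms that the standard errors are simply too small, or that ignoring exercise groups inflates the error rate. The documents support neither reading, because site-robust errors are specified and groups meeting within a site are covered. A reader might also attribute the whole inflation under a normal reference to omitted provider clustering. Step 4 shows that much of it is there without any.

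Nor can one say that health-worker contact was confined to the intervention arm. As worded, workers evaluated symptoms every other week, and that assessment was given in both arms. Only delivery of the therapy is specific to the intervention arm. Home use of the exercise video further weakens group clustering.

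The reply does not dispose of the cross-site case. Recruitment from a central unit, phone delivery and four languages of delivery all make crossing possible, and nothing in the plan excludes it. Step 2 assumes nesting, so it cannot settle the question.

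**Conclusion.** The point holds conditionally. The site-robust errors cover exercise-group and health-worker clustering within a site. They do not cover workers who treated at several sites, which is possible but undocumented. Under the assumed ICCs, caseload and site counts, the corrected test's type I error would be about 5-6.5% with 25-50% crossing and about 6-9% with full crossing. Full crossing is an extreme that sits poorly with recruitment from each community organization.

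The missing small-sample reference matters at least as much over the assumed range: about 7-10% at 6-15 sites with no crossing. It cannot be sized for this trial because the number of sites is not stated, and unequal site sizes would make it worse. These findings support a sensitivity analysis beside the primary model, not its replacement.

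**What to change.** 1. Keep the site-robust primary model, but name a small-sample reference, for example t on sites minus 1.
2. State the numbers of sites, health workers and exercise groups, and check from session records whether any worker treated at more than one site.
3. Add a sensitivity analysis to equation (1): a health-worker random effect multiplied by Intervention_i (all outcomes) and an exercise-group effect multiplied likewise (SPPB, LLFDI, WHODAS 2.0), with small-sample degrees of freedom. Report the ICCs.
4. Before treating control participants as singletons, confirm who carried out their symptom assessments. If the same workers did, say how that contact is handled.

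**Cost.** No new data if session records hold worker and group identifiers, as they should. The sensitivity analysis would give slightly wider intervals, and a variance may be estimated as zero, in which case that term drops out. The t reference costs more when sites are few: against 1.96, the multiplier is 2.571 at 6 sites (31% wider), 2.262 at 10 (15%) and 2.145 at 15 (9%).
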